**4.3.1. Study discontinuation (if applicable) n/a**

**4.3.2. Concomitant medication (if applicable) n/a**

**4.4. Risks and Benefits**

**4.4.1. Risks**

As this study proposes tobacco cessation, risks to participants are deemed minimal. There is a potential risk of loss of confidentiality but that is protected against by coding all data with study IDs only, presenting results of statistical analyses only in aggregate form, and limiting the use of the data to research staff who are IRB approved to participate in the research, have been trained in methods of maintaining confidentiality, and have completed training in the protection of human subjects and research integrity at regular intervals.

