5	Addresses Stress Management (same)	Addresses Stress Management (same)

Study Number: Pro2022-0894	05.02.2023
----------------------------	------------

6	Addresses Weight and African Americans, Smoking and Weight Concerns, Minimizing Weight Gain, Healthy Eating within a Soul Food Diet including Recipes	Minimizing Weight Gain
---	---	------------------------

During the Week 1 telephone call with the CTTS, the participant will be educated about combination nicotine replacement therapy over-the-counter medication and the Nicotine Replacement Therapy (NRT) patch kit + NRT lozenge kit will be mailed to the participant's home.

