**5.3. Study intervention (including schedule of events and study visits)**

The study intervention includes a combination of tobacco treatment counseling sessions using motivational interviewing by certified tobacco treatment specialists, randomization to either (a) culturally-tailored tobacco treatment intervention or (b) preference driven culturally-tailored tobacco treatment intervention, home CO monitoring, and combination

Study Number: Pro2022-0894	05.02.2023
----------------------------	------------

nicotine replacement therapy over-the-counter medication and the Nicotine Replacement Therapy (NRT) patch kit + NRT lozenge kit.

After a participant is consented and enrolled into the study, they will complete a baseline survey and be scheduled for weekly telephone calls with a certified tobacco treatment specialist. After the baseline survey is completed, a personal home CO monitor will be ordered for the patient and shipped directly to their home. Instructions on how to use will be emailed to the participant and reviewed in the 1st weekly counseling session with the CTTS.

The tobacco intervention content will be delivered by telephone by a CTTS weekly. The weekly activities including plan to reduce total cigarette intake, and dosing chart for the nicotine replacement (based upon the National Comprehensive Cancer Network's Evidence-Based Tobacco Treatment Guidelines (2022) is listed below by week:

Week	Tobacco Intervention Content	Nicotine Replacement Therapy
Orientation (Baseline)	
 
Overview of Study
 
Informed Consent
 
Baseline Surveys
 
	
Dosing Chart
 
>10cigarettes/day: Initially one 21mg patch daily for 6 weeks; then one 14mg patch daily for 2 weeks, then one 7mg patch daily for 2 weeks, then stop.
 
≤10cigarettes/day: initially one 14mg patch daily for 6 weeks then one 7mg patch daily for 2 weeks, then stop.

Session 1	
 
Review Quit Plan
 
Baseline CO Level
 
	
Session 2	
 
Behavior Target: Decrease # of Cigarettes Daily by 20%
 
	
 
Start NRT: Nicotine Patch (see dosing chart) + 2mg NRT lozenges prn
 

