Session 3	
 
Behavior Target: Decrease # of Cigarettes Daily by additional 20% (total = 40%)
 
	
 
Continue NRT: Nicotine Patch (see dosing chart) + 2mg NRT lozenges prn
 

Session 4	
 
Behavior Target: Decrease # of Cigarettes Daily by additional 20% (total = 60%)
 
	
 
Continue NRT: Nicotine Patch (see dosing chart) + 2mg NRT lozenges prn
 

Session 5	
 
Behavior Target: Decrease # of Cigarettes Daily by additional 20% (total = 80%)
 
	
 
Continue NRT: Nicotine Patch (see dosing chart) + 2mg NRT lozenges prn
 

Session 6	
 
Behavior Target: Decrease # of Cigarettes Daily by additional 20% (total = 100% = QUIT)
 
	
 
Continue NRT: Nicotine Patch (see dosing chart) + 2mg NRT lozenges prn
 

Final Session	
 
Assess how participant is doing. How many cigarettes (if any) smoking per day. Answer any questions including questions about NRT tapering schedule
 
Assess NRT use, response, issues
 
	
 
Taper NRT per protocol
 

During the Week 1 telephone call with the CTTS, the participant will be educated about combination nicotine replacement therapy over-the-counter medication and the Nicotine Replacement Therapy (NRT) patch kit + NRT lozenge kit will be mailed to the participant's home.

The 6 tobacco treatment counseling sessions will use motivational interviewing by a CTTS to address quitting motivations, benefits of tobacco treatment, overcoming nicotine dependence and practical ways to handle triggers, nicotine withdrawal management, stress management, healthy eating and activity, and relapse prevention.

Study Number: Pro2022-0894	05.02.2023
----------------------------	------------

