#### 5.4. Assignment / randomization (if applicable) n/a

#### 5.5. Section of instruments.

The primary outcome of this feasibility and usability pilot study is satisfaction with the processes of the study. A Satisfaction and Usability Questionnaire will be used that assesses participant thoughts and opinions about the intervention components, duration, outreach, and methods.

In addition, we will assess sociodemographic data including gender, race, marital status, education, and employment status will be gathered along with data on health status, history of chronic disease, and height and weight. Nicotine addiction will be measured by the Fagerström Questionnaire. Stage of change for smoking will be assessed uses the processes of change, self-efficacy for behavior change, and decisional balance (pros and cons of change). *Biochemical Validation*. Expired carbon monoxide measures will be used to confirm smoking status. CO levels < 9 ppm will be used as the cutoff.

Timing of Assessments	Baseline	Weekly	6 weeks post study start
Sociodemographic & Health Status Questionnaire	X		
Fagerstrom Test for Nicotine Dependence	X	X	X
CO Monitor	X	X	X
Stage of Change for Tobacco Cessation	X		X
Usability			X
Acceptance & Satisfaction			X

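### Section 4.4.1 omits nicotine replacement therapy from the risks, and the only scheduled enquiry about problems with it comes at the Final Session

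*Combined protocol and SAP*

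**What the plan says.** Section 4.4.1 (Risks) reads "As this study proposes tobacco cessation, risks to participants are deemed minimal". It then names one specific risk, loss of confidentiality, and how that is controlled. NRT is not mentioned there.

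NRT is nevertheless part of the intervention in both arms. Section 4.3 (Intervention Content) states that "the Nicotine Replacement Therapy (NRT) patch kit + NRT lozenge kit will be mailed to the participant's home". Section 5.3 gives a patch dosing chart (21 mg or 14 mg a day to begin with, depending on cigarettes per day). Its session table then sets out:

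- Session 2: "Start NRT: Nicotine Patch (see dosing chart) + 2mg NRT lozenges prn", beside "Behavior Target: Decrease # of Cigarettes Daily by 20" per cent.
- Sessions 3 to 6: "Continue NRT: Nicotine Patch (see dosing chart) + 2mg NRT lozenges prn", with a further 20% cut at each session. At Session 6 the target is "Decrease # of Cigarettes Daily by additional 20% (total = 100% = QUIT".
- Final Session: "Assess NRT use, response, issues". This entry appears nowhere else in the table.

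The assessment table in section 5.5, headed "Timing of Assessments", has six rows: sociodemographic and health status, Fagerström, CO, stage of change, usability, and acceptance and satisfaction. Section 6.4 lets participants withdraw at any time. Section 5.8.2 makes all analysis descriptive and names no safety summary.

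**The concern.** The reason given in section 4.4.1 for minimal risk is that the study aims at cessation. That does not address the products the study itself mails out and doses. The risk may well be small, but the section does not mention it.

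The schedule matters more in practice. Women start a patch and lozenges at Session 2 while still smoking by design, and the plan does not ask how they are tolerating them until the end. A woman who has a problem, stops NRT and leaves before the Final Session never gets the question. The study could then finish with an incomplete account of who had trouble with NRT or stopped it. That information would help protect participants during the study and would be useful for the larger study that section 3.1 says this pilot supports.

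**Working it through.** The plan gives no figure on this point to reproduce, so the check compares the schedule with the places where a record could be made.

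**1. Contacts after the NRT start (section 5.3).** NRT starts at Session 2, so no problem with it can be reported at that call. The contacts listed afterwards are Sessions 3, 4, 5, 6 and the Final Session: 4 + 1 = 5. The enquiry is listed at one of them, so 1 of 5. The text of section 5.3 speaks of six counselling sessions and does not say whether the Final Session is a separate call. If it is held with Session 6, the contacts are Sessions 3, 4, 5 and the combined one, so 1 of 4.

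**2. Follow-up sessions at which smoking is still expected (section 5.3).** Remaining smoking = 100% − cumulative reduction target.

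| Session | Cumulative target | Remaining | NRT enquiry listed |
|---|---|---|---|
| 2 (NRT starts) | 20% | 80% | not yet relevant |
| 3 | 40% | 60% | no |
| 4 | 60% | 40% | no |
| 5 | 80% | 20% | no |
| 6 | 100% | 0% | no |
| Final | – | – | yes |

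Follow-up sessions with a remaining target above zero: 3, 4 and 5. The enquiry is at 0 of these 3.

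**3. Where a problem could be recorded.**

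- Section 5.5 table: 0 of the 6 row titles concern NRT or adverse events. This counts titles only; the items themselves are not visible.
- Satisfaction and Usability Questionnaire (section 5.5): covers opinions on the intervention components. Section 5.3 lists NRT among these, so NRT could come up. It is given at 6 weeks, and section 5.6 has the end-of-study interview entered in REDCap.
- Section 6.5: the monitoring described concerns the online processes and REDCap, not participant harms.
- Sections 4.2.4 (withdrawal criteria), 4.3.1 (study discontinuation) and 4.3.2 (concomitant medication) are marked not applicable, so none of them provides a record.
- Final Session enquiry: the plan does not say on what form the answer is kept.

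**4. Early leavers.** Both the Final Session enquiry and the questionnaire come at the end. Section 6.4 allows withdrawal at any time, and no enquiry is scheduled at withdrawal. The documents give no drop-out rate and no rate of NRT problems, so the number of women affected cannot be estimated.

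**The case against.** The case for leaving the plan alone is a fair one. The products are over the counter, and dosing is stated to follow a 2022 national guideline. Women who are pregnant or have cardiovascular disease, lung disease or mental illness are excluded. A tobacco treatment specialist calls every week, teaches NRT use in Week 1 and reinforces it in Week 2, and withdrawal management is a counselling topic. The first newsletter, in both the active and passive versions, deals with concerns about NRT. The Final Session enquiry can also bring out earlier problems in retrospect. No aim depends on NRT tolerability.

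Most of this stands, and it keeps the severity low. It lowers the risk and makes it likely that many problems will be mentioned. It does not provide a scheduled question before the end, a stated place to record the answer, or any enquiry for women who leave early.

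A reader might infer three stronger things that the documents do not support:

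- *That nothing about NRT problems will be recorded.* The 6-week questionnaire may pick some up from women who reach that point. Appendix 1 (Measures) is listed but not shown and may contain a relevant item.
- *That participants are not told of NRT risks.* The consent form is not among the available pages, so its content cannot be held against the plan.
- *That smoking while using the patch and lozenges is shown to be harmful here.* The documents give no harm threshold or event rate. The reduction targets show only that NRT and smoking overlap by design.

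**Conclusion.** The point holds as a modest gap in risk description and safety recording. Section 4.4.1 leaves out the medication that the study supplies. The scheduled NRT enquiry falls at 1 of 5 contacts after the start (1 of 4 if the Final Session is combined with Session 6) and at 0 of the 3 follow-up sessions where smoking is still expected. Problems in the early sessions rest on informal mention or later recall, and women who withdraw early are not asked.

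This assumes that the session table in section 5.3 lists all planned NRT enquiries, and that the unseen Appendix 1 and consent form do not already fill the gap. It would be wrong to go further and say that a result of the trial is distorted: NRT tolerability is not a stated outcome, the analysis is descriptive, no stated estimate is biased and no effect size is claimed. Severity is low, with medium confidence.

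**What to change.** - Ask the enquiry already written for the Final Session ("Assess NRT use, response, issues") at each weekly call from Session 3 and, where the woman agrees, at withdrawal.
- Record the answer, and whether NRT was stopped, on a short REDCap form, and add a row for it to the section 5.5 table.
- Report the counts descriptively, with all women sent NRT as the denominator (at most the planned 20, since both arms receive it).
- Name NRT side effects in section 4.4.1.
- If Appendix 1 or the consent form already covers any of this, a cross-reference in sections 4.4.1 and 5.5 is enough for that part.

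The cost is slightly longer calls and one extra form. The calls are already scheduled, CO and Fagerström are already assessed weekly, and REDCap is already in use.

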**4.4.2. Benefits**

Potential benefits are tobacco cessation for participants.

## 5 – Methods

**5.1. Screening**

This is a community-based feasibility and usability study. As such, recruitment procedures will be community-based and described below.

**5.2. Recruitment, enrollment, and retention (including screen failures as applicable)**

We will recruit participants using informal recruitment through social networks and community-based advertisements/media (advertisements, neighborhood flyers) in New Jersey.

The weekly intervention calls with the CTTS will assist with retention in this 6-week study. In addition, the weekly content newsletter will assist with retention secondary to actively engaging participants during the course of the study.

**5.3. Study intervention (including schedule of events and study visits)**

The study intervention includes a combination of tobacco treatment counseling sessions using motivational interviewing by certified tobacco treatment specialists, randomization to either (a) culturally-tailored tobacco treatment intervention or (b) preference driven culturally-tailored tobacco treatment intervention, home CO monitoring, and combination

Study Number: Pro2022-0894	05.02.2023
----------------------------	------------

nicotine replacement therapy over-the-counter medication and the Nicotine Replacement Therapy (NRT) patch kit + NRT lozenge kit.

After a participant is consented and enrolled into the study, they will complete a baseline survey and be scheduled for weekly telephone calls with a certified tobacco treatment specialist. After the baseline survey is completed, a personal home CO monitor will be ordered for the patient and shipped directly to their home. Instructions on how to use will be emailed to the participant and reviewed in the 1st weekly counseling session with the CTTS.

The tobacco intervention content will be delivered by telephone by a CTTS weekly. The weekly activities including plan to reduce total cigarette intake, and dosing chart for the nicotine replacement (based upon the National Comprehensive Cancer Network's Evidence-Based Tobacco Treatment Guidelines (2022) is listed below by week:

Week	Tobacco Intervention Content	Nicotine Replacement Therapy
Orientation (Baseline)	
 
Overview of Study
 
Informed Consent
 
Baseline Surveys
 
	
Dosing Chart
 
>10cigarettes/day: Initially one 21mg patch daily for 6 weeks; then one 14mg patch daily for 2 weeks, then one 7mg patch daily for 2 weeks, then stop.
 
≤10cigarettes/day: initially one 14mg patch daily for 6 weeks then one 7mg patch daily for 2 weeks, then stop.

Session 1	
 
Review Quit Plan
 
Baseline CO Level
 
	
Session 2	
 
Behavior Target: Decrease # of Cigarettes Daily by 20%
 
	
 
Start NRT: Nicotine Patch (see dosing chart) + 2mg NRT lozenges prn
 

Session 3	
 
Behavior Target: Decrease # of Cigarettes Daily by additional 20% (total = 40%)
 
	
 
Continue NRT: Nicotine Patch (see dosing chart) + 2mg NRT lozenges prn
 

Session 4	
 
Behavior Target: Decrease # of Cigarettes Daily by additional 20% (total = 60%)
 
	
 
Continue NRT: Nicotine Patch (see dosing chart) + 2mg NRT lozenges prn
 

Session 5	
 
Behavior Target: Decrease # of Cigarettes Daily by additional 20% (total = 80%)
 
	
 
Continue NRT: Nicotine Patch (see dosing chart) + 2mg NRT lozenges prn
 

Session 6	
 
Behavior Target: Decrease # of Cigarettes Daily by additional 20% (total = 100% = QUIT)
 
	
 
Continue NRT: Nicotine Patch (see dosing chart) + 2mg NRT lozenges prn
 

Final Session	
 
Assess how participant is doing. How many cigarettes (if any) smoking per day. Answer any questions including questions about NRT tapering schedule
 
Assess NRT use, response, issues
 
	
 
Taper NRT per protocol
 

During the Week 1 telephone call with the CTTS, the participant will be educated about combination nicotine replacement therapy over-the-counter medication and the Nicotine Replacement Therapy (NRT) patch kit + NRT lozenge kit will be mailed to the participant's home.

The 6 tobacco treatment counseling sessions will use motivational interviewing by a CTTS to address quitting motivations, benefits of tobacco treatment, overcoming nicotine dependence and practical ways to handle triggers, nicotine withdrawal management, stress management, healthy eating and activity, and relapse prevention.

Study Number: Pro2022-0894	05.02.2023
----------------------------	------------

#### 5.4. Assignment / randomization (if applicable) n/a

#### 5.5. Section of instruments.

The primary outcome of this feasibility and usability pilot study is satisfaction with the processes of the study. A Satisfaction and Usability Questionnaire will be used that assesses participant thoughts and opinions about the intervention components, duration, outreach, and methods.

In addition, we will assess sociodemographic data including gender, race, marital status, education, and employment status will be gathered along with data on health status, history of chronic disease, and height and weight. Nicotine addiction will be measured by the Fagerström Questionnaire. Stage of change for smoking will be assessed uses the processes of change, self-efficacy for behavior change, and decisional balance (pros and cons of change). *Biochemical Validation*. Expired carbon monoxide measures will be used to confirm smoking status. CO levels < 9 ppm will be used as the cutoff.

Timing of Assessments	Baseline	Weekly	6 weeks post study start
Sociodemographic & Health Status Questionnaire	X		
Fagerstrom Test for Nicotine Dependence	X	X	X
CO Monitor	X	X	X
Stage of Change for Tobacco Cessation	X		X
Usability			X
Acceptance & Satisfaction			X

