### 3.2. Hypothesis (if applicable)

- 1) Participants will report the 6-week tobacco treatment intervention is acceptable and they are satisfied with the intervention.
- 2) Participants who complete the preference driven culturally-tailored tobacco treatment intervention will have higher rates of tobacco abstinence compared to participants in the control arm.

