### 3.4. Primary Outcome Variable(s)

Feasibility, acceptability and satisfaction with the content of the educational content and the tobacco treatment intervention.

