## 4 - Study Design

### 4.1 General Design

The overall study design is a 6-week community-based tobacco treatment intervention to address tobacco use in the African American female community. This pilot study is testing the feasibility, acceptability and satisfaction of a 6-week community-based culturally-tailored tobacco treatment intervention to a preference driven culturally-tailored tobacco treatment intervention targeted to African American women in New Jersey with 20 African American women; 10 participants will receive the culturally-tailored tobacco treatment intervention and 10 participants will complete the one-item Control Preference Scale and receive preference driven culturally-tailored tobacco treatment intervention based upon their control preference.

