#### 5.6. Data management (data collection, source and storage)

Data at baseline and end of study (6 weeks post study start for each participant) will be collected by phone. Self-report data will be gathered via a standardized interview using REDCap (Research Electronic Data Capture). REDCap is a secure web-based application for building and managing online surveys and databases. REDCap provides audit trails for tracking data manipulation and user activity as well as export procedures for secure data downloads to common statistical packages.

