#### 5.7. Follow-up and end-of study (if applicable) n/a

#### 5.8. Statistical Method

**5.8.1. Sample size calculation and justification** N/A (this is a feasibility and usability pilot study with 20 participants)

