### **6.4. Informed consent**

Participants are invited via community-based recruitment flyers and advertisements. Participants who contact the study office will be screened by telephone for inclusion and exclusion criteria. During the telephone screening, the study personnel will speak with the individual to determine that they can give informed consent for themselves. At that time, the study personnel will read through and discuss the informed consent with the individual. Once they have finished discussing the informed consent, the individual will be given an opportunity to ask any questions they may have. The study personnel will stress that the individual can withdraw from the study at any time with no penalty. The individual will then be asked to provide verbal informed consent and enroll in the study, or to decline to participate. If the individual provides verbal informed consent, a copy of the consent form will either be emailed or mailed to their home for their records.

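### Satisfaction, the primary outcome, is scheduled only at week 6, with no exit assessment and no stated denominator, so a responders-only figure is liable to overstate it

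*Combined protocol and SAP*

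**What the plan says.** Section 5.5 states: "The primary outcome of this feasibility and usability pilot study is satisfaction with the processes of the study". Section 3.4 words the primary outcome more broadly: "Feasibility, acceptability and satisfaction with the content of the educational content and the tobacco treatment intervention". The first hypothesis in section 3.2 is that "Participants will report the 6-week tobacco treatment intervention is acceptable and they are satisfied with the intervention".

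In the timing table of section 5.5, the usability row and the "Acceptance & Satisfaction" row are marked only in the column for 6 weeks after study start. The Fagerström test and the CO reading are marked weekly as well. Section 5.6 adds: "Data at baseline and end of study (6 weeks post study start for each participant) will be collected by phone".

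On leaving early, section 6.4 has staff stress that "the individual can withdraw from the study at any time with no penalty". Sections 4.2.4 (withdrawal), 4.3.1 (discontinuation) and 5.7 (follow-up) are entered as not applicable. The retention measures named in section 5.2 are the weekly calls and the newsletters.

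On analysis, section 5.8.2 is a single sentence limiting the analysis to description. It gives no analysis set, denominator or rule for missing answers. On allocation, section 4.1 says "10 participants will receive the culturally-tailored tobacco treatment intervention and 10 participants will complete the one-item Control Preference Scale".

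**The concern.** Missing answers here are not a routine nuisance. Finding a programme unacceptable is a plausible reason to leave it, so whether a woman answers at week 6 may depend on the very thing being measured. The retention measures are also components of the programme under test, so a woman who dislikes the calls or newsletters is the one they are least likely to hold.

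If satisfaction is reported only among women who answer at week 6, the first hypothesis is examined in a group that may be selected towards agreeing with it. With 10 women per arm, each missing answer leaves 10 percentage points of that arm's result undetermined. Section 3.1 presents the pilot as support for a larger study, so a component that some women found unacceptable could be carried forward without the pilot showing it. With 20 women, opinions not collected at the time cannot be recovered later.

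**Working it through.** **No figure to reproduce.** The plan states no dropout rate, satisfaction threshold or precision. Its sample-size entry (5.8.1) reads "N/A (this is a feasibility and usability pilot study with 20 participants". What follows illustrates size under labelled assumptions.

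**Inputs from the documents.** 20 women, 10 per arm (4.1); satisfaction taken once, at week 6 (5.5).

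**Assumptions.** 2 to 8 of the 20 have no week-6 answer; about 90% of those who answer are satisfied.

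**Step 1: general size of the bias.** Let d be the share missing, s_c the proportion satisfied among women who answer, and s_l the proportion among those who do not.

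- Satisfaction in all women = (1 − d) × s_c + d × s_l
- Responders-only figure = s_c
- Overstatement = s_c − [(1 − d) × s_c + d × s_l] = d × (s_c − s_l)

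With s_c = 0.90:

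| Missing (d) | No leaver satisfied | Half of leavers satisfied | Leavers match completers |
|---|---|---|---|
| 2 of 20 (0.10) | 9 points | 4 points | 0 |
| 4 of 20 (0.20) | 18 points | 8 points | 0 |
| 6 of 20 (0.30) | 27 points | 12 points | 0 |
| 8 of 20 (0.40) | 36 points | 16 points | 0 |

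For example, 0.20 × (0.90 − 0) = 0.18 and 0.20 × (0.90 − 0.50) = 0.08.

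**Step 2: the same in whole women.** With x satisfied and m missing, the responder figure is x/(20 − m). The worst case over all 20 is x/20 and the best case is (x + m)/20. Taking x as the whole number nearest to 90% of responders:

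| Missing | Responders only | Worst case | Best case |
|---|---|---|---|
| 2 | 16/18 = 89% | 16/20 = 80% | 18/20 = 90% |
| 4 | 14/16 = 88% | 14/20 = 70% | 18/20 = 90% |
| 6 | 13/14 = 93% | 13/20 = 65% | 19/20 = 95% |
| 8 | 11/12 = 92% | 11/20 = 55% | 19/20 = 95% |

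Rounding to whole women makes these gaps differ slightly from Step 1: 87.5 − 70 = 17.5 points with 4 missing, against 18.

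**Step 3: against sampling error.** With 4 missing, the exact (Clopper-Pearson) 95% interval is 62% to 98% for 14/16 and 46% to 88% for 14/20. Both are wide. The worst-case shift adds to that uncertainty, and the interval around the responder figure does not reflect it.

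**Step 4: within one arm of 10.** With 2 missing, 7/8 = 88% among responders, bounds 7/10 = 70% to 9/10 = 90%. With 3 missing, 6/7 = 86%, bounds 60% to 90%.

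**The case against.** The strongest counter-argument is section 5.6. The end interview is timed from study start and worded as applying to each participant. Stopping the calls is not the same as withdrawing from the study, and a woman who stops but can be reached is still due her interview. A reader might infer from the timing table that every woman who stops early is excluded from the outcome. The documents do not support that. The gap is confined to women who withdraw or cannot be reached.

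A reader might also infer that satisfaction will be overstated, or that the plan specifies a completers-only analysis. Neither is written. Overstatement needs both missing week-6 answers and lower satisfaction among those missing. The documents give neither a dropout rate nor reasons for leaving, and reasons unrelated to acceptability would produce little or no bias. Section 5.8.2 is silent on the denominator, which is different from choosing completers. It is likewise possible, but speculative, that unequal loss would make the less acceptable arm look better.

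Two further points stand in part. Feasibility is also named as primary (3.4), and attrition would naturally be read there, but no retention or call-completion measure is defined. Week 6 is also a sensible time to rate a six-week programme as a whole, so the week-6 assessment should stay. The three not-applicable entries are template fields and weak evidence alone. What matters is that no exit assessment appears anywhere.

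None of this closes the gap. Section 5.6 sets timing and mode. It does not commit staff to pursue women who have stopped, it cannot reach those who have withdrawn, and it says nothing about reporting.

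**Conclusion.** The point holds as a risk created by the schedule and by the silence on reporting. It does not establish that bias will occur. The primary outcome is taken once, women who withdraw or are lost have no route to contribute, and nothing in the plan prevents a responders-only percentage.

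The 18-point figure is a worst case. It rests on three assumptions outside the documents: 4 of 20 missing, 90% of completers satisfied, and no satisfied leaver. The 8-point figure keeps the first two and supposes half of leavers satisfied. If nobody is missing, or leavers match completers, there is no overstatement.

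The pilot can run as planned, but its main result would be hard to interpret if several women were lost. The change should be made because it is cheap and cannot be made retrospectively.

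**What to change.** **Sections 5.5 and 5.6 (collection).**
- Offer the existing Satisfaction and Usability Questionnaire at last contact to any woman who withdraws and is willing to answer.
- State that the week-6 interview will be attempted in every randomised woman regardless of how many calls she took. Preferably someone other than her own counsellor asks the questions, where such staff are already available, to limit courtesy answers.

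**Section 5.8.2 (reporting).**
- Report satisfaction by arm over all randomised women (10 per arm). Give the responder figure, the number of non-responders, and the bounds with all non-responders counted as satisfied and all counted as not satisfied. Showing both bounds is more neutral than simply treating an unreachable woman as dissatisfied.
- Beside it, report calls completed and retention as the feasibility result.

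**Cost.** A few extra phone contacts, with no new instrument, visits or participants. The satisfaction figure will probably look less favourable, and women who decline any further contact will remain missing, which the bounds will show.
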